1.34.3 Consent of Subjects who are, or become, decisionally impaired

Not applicable. Adults unable to provide consent are excluded from enrolling in the protocol. However, it is possible that subjects enrolled in the protocol may permanently lose the capacity to consent for themselves during the course of this study. In the event this occurs, the subjects will be withdrawn from the study.

Abbreviated Title: Liraglutide in Teens Post-SG

Version Date: 1/30/23

1.35 STUDY DISCONTINUATION AND CLOSURE

This study may be temporarily suspended or prematurely terminated if there is sufficient reasonable cause. Written notification, documenting the reason for study suspension or termination, will be provided by the suspending or terminating party to study participants, investigator, funding agency, and regulatory authorities. If the study is prematurely terminated or suspended, the Principal Investigator (PI) will promptly inform study participants, the Institutional Review Board (IRB), and NICHD Clinical Director and will provide the reason(s) for the termination or suspension. Study participants will be contacted, as applicable, and be informed of changes to study visit schedule.

Circumstances that may warrant termination or suspension include, but are not limited to:

- Determination of unexpected, significant, or unacceptable risk to participants
- Insufficient compliance to protocol requirements
- Data that are not sufficiently complete and/or evaluable

Study may resume once concerns about safety, protocol compliance, and data quality are addressed, and satisfy the NICHD Clinical Director, IRB and, as applicable, the Food and Drug Administration (FDA).

1.36 CONFIDENTIALITY AND PRIVACY

Participant confidentiality and privacy is strictly held in trust by the participating investigators and their staff. This confidentiality is extended to cover testing of biological samples and genetic tests in addition to the clinical information relating to participants. Therefore, the study protocol, documentation, data, and all other information generated will be held in strict confidence. No information concerning the study or the data will be released to any unauthorized third party without prior written approval of the Principal Investigator.

All research activities will be conducted in as private a setting as possible.

The study monitor, other authorized representatives of the NICHD Clinical Director, representatives of the Institutional Review Board (IRB), and/or regulatory agencies may inspect all documents and records required to be maintained by the investigator, including but not limited to, medical records (office, clinic, or hospital) and pharmacy records for the participants in this study. The clinical study site will permit access to such records.

The study participant's contact information will be securely stored for internal use during the study. At the end of the study, all records will continue to be kept in a secure location for as long a period as dictated by the reviewing IRB, Institutional policies, or NICHD requirements.

Samples and data will be coded. Human biospecimens will be collected using procedures appropriate for the type of biospecimen being collected and will be handled in accordance with the U.S. Occupational Safety and Health Administration's Bloodborne Pathogens Standard for Samples. The principal investigator and the co-investigators will have access to identifiable participant records. Data will be coded by subject number but will be readily associated with identifiable participant records. Records containing personal identifiers will be maintained consistent with the security measures required by the NIH. All NIH data will be kept on secure computers in the SGO office, whose doors will be locked when staff is not present. All paper data will also be kept in locked areas in the SGO office. Serum and plasma samples not analyzed

Abbreviated Title: Liraglutide in Teens Post-SG

Version Date: 1/30/23

immediately (as described above) NIH will be stored indefinitely in locked freezers by the NICHD sample management team supervised by the NICHD Clinical Director and tracked/managed through the NICHD Clinical Trials Database (CTDB). Human biospecimens in NICHD storage will have a unique identifier, will be labeled with a printed label and will contain a barcode. Samples will be tracked using a computer-based inventory system that records the location and detailed information of every specimen in the repository

Study participant research data, which is for purposes of statistical analysis and scientific reporting, will be transmitted to and stored in CTDB. Individual participants and their research data will be identified by a unique study identification number. The study data entry and study management systems used by research staff will be secured and password protected.

To further protect the privacy of study participants, a Certificate of Confidentiality has been issued by the National Institutes of Health (NIH). This certificate protects identifiable research information from forced disclosure. It allows the investigator and others who have access to research records to refuse to disclose identifying information on research participation in any civil, criminal, administrative, legislative, or other proceeding, whether at the federal, state, or local level. By protecting researchers and institutions from being compelled to disclose information that would identify research participants, Certificates of Confidentiality help achieve the research objectives and promote participation in studies by helping assure confidentiality and privacy to participants.

1.37 FUTURE USE OF STORED SPECIMENS AND DATA

Stored samples, specimens or data may be sent to collaborators for specific measurements or analyses. All stored samples, specimens, and data will be coded so that when sent for measurements the identity of the volunteer remains confidential. Identification of coded samples will be kept in a secure, password-protected database accessible only to investigators, but will be identifiable in case specific tests yield clinical information of importance to a particular volunteer or samples can be destroyed per volunteer request (see below). Samples will be used only for research and not for commercial purposes. Research volunteers will not be informed of individual results from analyses performed specifically for research purposes, unless there is clear evidence accepted by the medical community that these results would impact the volunteer's individual medical care or future health. Samples will be stored until used and will not be destroyed unless specifically requested in writing by the volunteer.

Additional consent will be obtained to use samples for purposes not already specified if participants have requested such consent be obtained (see consent form). Prior to transfer of samples and data to other (additional) non-NIH collaborators, a material transfer agreement (MTA) with the outside institution will be established. The PI will provide the IRB with a listing of MTA's that have been established under these provisions at the time of the Continuing Review and include a record of each such collaboration in the study protocol.

Staff will report to the Principal Investigators any destroyed samples, if samples become unsalvageable because of environmental factors (ex. Broken freezer or lack of dry ice in a shipping container), lost in transit between facilities or misplaced by a researcher. The PI will record any loss or unanticipated destruction of samples as a deviation.

Abbreviated Title: Liraglutide in Teens Post-SG

Version Date: 1/30/23

1.38 SAFETY OVERSIGHT

The clinical research team will meet on a weekly basis when participants are being actively treated on the trial to discuss progress and adverse events. All data will be collected in a timely manner and reviewed by the principal investigator or a lead associate investigator. Adverse events will be reported as required above. Events meeting requirements for expedited reporting will be submitted within the appropriate timelines.

Safety oversight will be under the direction of a Clinical Safety Officer (CSO) who is a Licensed Independent Practitioner (LIP) with relevant clinical experience. The CSO will be independent and not otherwise involved in the conduct of the trial. The NICHD Clinical Director and the Director of Clinical Research and Compliance, or their designees, will approve the selected CSO. The CSO and the PI will jointly determine an interval for routine safety monitoring appropriate for the risk level of the trial. This will be included as part of the monitoring plan in the clinical study protocol along with appropriate study stopping rules. The PI is responsible for promptly notifying the CSO of any emerging safety signals. The CSO will review all Dose-Limiting Toxicities (DLTs) considered to be at least possibly related to the study drug, instances of dose reductions due to intolerance, as well as any emerging safety signals identified by the PI on an ad hoc basis. All Adverse Events, including those that are expected, will be described in the routine safety monitoring reports reviewed by the CSO. If there are unresolved differences regarding adverse event causality assessment, event reporting, or management, the NICHD Clinical Director and the Director of Clinical Research and Compliance, or their designees, will be notified and asked to adjudicate. The CSO will provide its input to the Clinical Director of NICHD and other staff as appropriate.

For this pilot study of a medication that is FDA-approved for the age group investigated, that is performed under an FDA exemption, it is anticipated that the chance of unexpected AEs that would lead to study discontinuation is low. Therefore, it is proposed that the routine report that the CSO will review that includes all AEs will occur once yearly, at the time of Continuing Review. As specified above, SAEs will be reported promptly to the CSO independent of this scheduled report.

After half of all anticipated subjects (i.e. at n=20) have had the opportunity to take study medication for the 16-week treatment period, the CSO will review the percentage of enrolled subjects who continued to take study medication through the 16 week (primary efficacy) timepoint. If fewer than 50% remain in the per protocol dataset, the study will be stopped.

The study will also be reviewed to determine if it should be stopped if 3 or more study subjects develop unexpected SAEs that are assessed as probably related to study medication or if 6 or more study subjects develop expected or unexpected SAEs that are assessed as probably related to study medication.

Individual study subject stopping rules have also been established (see attached file titled, "CTCAE_v5.0_2017-11-27 for Liraglutide - revised 2021-FEB-24". In general, a participant will at a minimum reduce the dose and, in most instances, not continue study medication if they develop CTCAE 5 grade 3 or greater adverse events, but in some categories lower grades will lead to consideration of medication discontinuation.

Abbreviated Title: Liraglutide in Teens Post-SG

Version Date: 1/30/23

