1.9 JUSTIFICATION FOR DOSE

Eligible patients will be treated with daily subcutaneous liraglutide (starting at 0.6 mg daily with weekly dose escalations up to 3.0 mg per day or max tolerated dose). This dose is in line with liraglutide's treatment dose for adults with a BMI ≥ 30 kg/m² or BMI ≥ 27 kg/m² with at least one weight-related comorbidity (dose 3 mg daily).

Abbreviated Title: Liraglutide in Teens Post-SG

Version Date: 1/30/23

In addition, a recent randomized, double-blind, placebo-controlled phase 3 trial of liraglutide for adolescents (age 12 to <18 years) with obesity (BMI ≥ 30 kg/m² and $\geq 95^{\text{th}}$ percentile for age and sex) used a treatment dose of 3.0 mg daily [32] and had a comparable safety and tolerability profile to trials in adults with obesity with no new safety issues [49].

STUDY POPULATION

Adolescents are selected as the study subjects because of the dearth of relevant data for adolescents who have undergone SG. All races and ethnicities will be included. Since obesity is identified in large percentages among minority groups including Asian Americans, African American and Hispanic Americans, we anticipate good representation of all major races/ethnicities. It is expected, given our recruitment procedures targeting individuals living in the greater metropolitan Washington, D.C. area, that we will recruit rates of minority participation in excess of their representation in the Washington, D.C. metropolitan area: 64.2% Caucasian, 27.2% African American and 8.6% Hispanic.

Total number of subjects to be studied in the protocol: 50 maximum

Planned number of subjects to be screened in person: 50 maximum

Planned number of subjects to be treated with liraglutide: 43 maximum

Subjects will not be replaced if they withdraw or become ineligible.

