1.16 STRATEGIES FOR RECRUITMENT AND RETENTION

Recruitment: A total of at most 50 participants to be screened at the NIH for protocol participation will be recruited from Washington, DC and local suburbs in Maryland and Virginia, with expected accrual rate of approximately 4 participants per month. Recruitment efforts will aim to enroll subjects in proportion to their representation in the population of Maryland. Subjects of all racial, ethnic and socio-economic backgrounds will be invited to participate in this study. Tools used for the recruitment of subjects will include the posting of the study description on the NIH Clinical Trials website. Additionally, flyers will be placed on bulletin boards at different buildings throughout the NIH campus and CNH. Recruitment material will be IRB approved prior to dissemination. Potential participants may also be referred by local providers responsible for clinical care. This includes providers from CNH's Bariatric Surgery Clinic and CNH's Obesity Program (multidisciplinary IDEAL Clinic) as well as from other community providers to whom we will provide our study information via a physician mailing letter and recruitment flyer. If necessary, further subjects will be recruited through newspaper advertisements or letter mailings. Advertisements will be submitted to the IRB before use.

Retention: There are incentives for attendance at study visits in terms of compensation for the time spent for, and inconvenience of, participation (see Compensation). We have a well-established track record of success in retaining participants with obesity for pharmacotherapy trials in adults and children [56-60]. For example, we recruited 340 adults for a 2-year pharmacotherapy RCT, retaining 82% for 1-year and 75% for 2-year study outcome measurements.

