1.31 SAMPLE SIZE DETERMINATION

As this is a pilot investigation to determine the sample size of a fully powered investigation, no formal sample size determination is necessary. That said, the study is powered such that it might be able to detect a moderate-to-large difference from treatment. A recent randomized, double-blind, placebo-controlled phase 3 trial of liraglutide for adolescents (age 12 to <18 years) with obesity ($BMI \geq 30 \text{ kg/m}^2$ and $\geq 95^{\text{th}}$ percentile for age and sex) [32] reported a -1.39 kg/m^2 ($SE=0.31$, $n=125$) difference over 1 year of liraglutide treatment. If that effect size is replicated and if a similar SD (3.46) is found in the present study, we estimate that a total sample size of 40 subjects will have 80% power (β) to detect a -1.39 kg/m^2 difference in BMI (effect size = -

Abbreviated Title: Liraglutide in Teens Post-SG

Version Date: 1/30/23

0.4017) at level of significance of 0.05 (1-sided, as we are interested only in BMI loss). See **Table 2**.

t-test - Means: Difference between two dependent means (matched pairs) Tails = 1, $\alpha = 0.05$, Effect size dz = 0.4

[figure not shown]

Table 2, drawn using data obtained using G-Power 3.1.9.2 [90, 91]

We anticipate that virtually all participants who sign consent and are screened will qualify and agree to enroll. We will therefore attempt to recruit and screen in person no more than 50 adolescents, among whom no more than 43 will be treated with liraglutide in hopes of having 40 who complete the study. Based on prior studies in adolescents using liraglutide, we anticipate few dropouts or withdrawals by week 16. In Kelly et al's study of adolescents [32], 119/125 (95%) of those treated with liraglutide remained on-treatment at week 16.

As a pilot investigation, there is no assumption that there will be adequate power for any of the secondary outcomes investigated. We will, however, be able to use the data to determine power in a future randomized controlled trial for these outcomes.

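### At the expected accrual, about 33 to 36 of 43 participants will have been dosed when the n=20 retention check falls due, and the check reviews one quantity but stops on another

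*Combined protocol and SAP*

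**What the plan says.** The check is in section 1.38 (Safety Oversight). Its timing is "After half of all anticipated subjects (i.e. at n=20) have had the opportunity to take study medication for the 16-week treatment period". At that point the Clinical Safety Officer (CSO) reviews the percentage of enrolled participants who continued on drug to week 16. The consequence follows in the next sentence: "If fewer than 50% remain in the per protocol dataset, the study will be stopped".

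The figures that determine when this falls due are elsewhere:

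- Section 1.16: "A total of at most 50 participants to be screened at the NIH for protocol participation will be recruited", "with expected accrual rate of approximately 4 participants per month".
- Section 1.31: "We anticipate that virtually all participants who sign consent and are screened will qualify and agree to enroll"; and "no more than 43 will be treated with liraglutide in hopes of having 40 who complete the study".
- Study Population: "Planned number of subjects to be treated with liraglutide: 43 maximum".
- Section 1.3 (Schedule of Activities): the week-16 visit is day 112, plus or minus 10 days.
- Section 1.1 (Synopsis): study duration 36 months; 28 weeks per participant.
- Section 1.32: the Per Protocol dataset requires at least 80% of study intervention on 80% of treatment days.

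No section pauses enrolment while the check is pending, and section 1.38 does not say whether stopping the study ends dosing in participants who are mid-treatment.

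**The concern.** The check is described as falling at half of the sample, but its trigger is the 20th participant's week 16, not the 20th first dose. Enrolment continues for those 16 weeks, so the number who have started drug is well above half when the rule can first act. If retention were failing, most of the planned adolescents would already have begun treatment.

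There is a separate problem of definition. The quantity the CSO is asked to review is continuation on drug; the quantity that stops the study is Per Protocol membership. A participant still injecting at week 16 with adherence below the Per Protocol bar counts as retained under the first and as lost under the second. The two can fall on opposite sides of 50%, and the consequence is mandatory. This holds at any accrual rate.

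**Working it through.** **Reproducing n=20.** It is half of the 40 in section 1.31. With dz = 1.39/3.46 = 0.4017, one-sided alpha 0.05 and n = 40, an exact paired t-test has power 0.803, which agrees with the stated 80%. So 20 = 40/2.

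**Number dosed when the check falls due.** The documents give no figure. Assuming uniform accrual and no pause:

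dosed = 20 + (first doses per month) × (days to the week-16 visit / 30.44)

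| Dosing rate | Days | Dosed | Undosed of 43 |
|---|---|---|---|
| 4 per month | 112 | 20 + 4 × 3.68 = 34.7 | 8.3 (19%) |
| 4 per month | 102 | 33.4 | 9.6 |
| 4 per month | 122 | 36.0 | 7.0 |
| 4 × 43/50 = 3.44 per month | 112 | 20 + 3.44 × 3.68 = 32.7 | 10.3 (24%) |
| 1.45 per month | 112 | 20 + 1.45 × 3.68 ≈ 25.4 | 17.6 (41%) |

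The 3.44 row reads the accrual rate as a screening rate, with 43 of 50 treated. The 1.45 row is an assumption: 43 participants spread over 36 months less 28 weeks of follow-up, 43/(36 − 6.44).

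In calendar terms, at 4 per month the 20th participant starts near 20/4 = 5.0 months and reaches day 112 near 5.0 + 3.68 = 8.7 months. All 43 would be dosed by 43/4 = 10.75 months.

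**Participants mid-course.** At 4 per month, 34.7 − 20 = 14.7 are on treatment at the check. If stopping the study also ended their dosing (not stated), with 8 weeks left on average, the exposure avoided is 14.7 × 8 + 8.3 × 16 ≈ 118 + 133 ≈ 250 of 43 × 16 = 688 patient-weeks, or 36%.

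**When the outcome is already settled.** Fewer than 50% of 20 means 9 or fewer, so 11 failures among the 20 fix the result. On 112 days, 80% is 89.6, so a participant with 23 missed days (89 taken) can no longer qualify. With the visit window the count moves: 21 missed days on 102 (80% is 81.6) and 25 on 122 (80% is 97.6).

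**Effect of acting at the 11th failure.** Simulated at 4 per month among runs where the rule is met. Failure is fixed 23 days after a participant stops. The failure rates and stopping times are assumptions. Mean number dosed, against about 35 under the current timing:

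| Stops spread over | Failure known | 70% fail | 60% fail |
|---|---|---|---|
| first 8 weeks | at once | 22 | 23 |
| first 89 days | at once | 24 | 26 |
| first 89 days | at the next monthly visit | 26 | 28 |

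At 1.45 per month the same approach gives about 17 to 20 dosed, against about 25.

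**How often the rule would be met.** The binomial chance that 11 or more of 20 fail is below 0.0001 at 10% failure, 0.0006 at 20% and 0.017 at 30%. Section 1.31 cites 119/125 (95%) on treatment at week 16 in the earlier adolescent trial.

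**The case against.** - **Sixteen-week retention cannot be seen before week 16.** Section 1.33.2 uses the same Per Protocol measure as a feasibility criterion, and section 1.38 never says that the rule exists to limit exposure. This stands as a reading of purpose. But failure can be known before week 16 even though success cannot, and the rule sits under safety oversight with a mandatory stop.
- **Thirty-five is near the high end.** The accrual rate is attached to those screened, and 4 per month would finish in about 17 months (10.75 months plus 28 weeks), far short of 36. This stands, and is why the range and the slow-accrual row are shown.
- **A reader might infer that the rule can spare almost no one.** The figures do not support that. Seven to 10 participants would never be dosed, up to about 18 under slow accrual, and about 15 more might have treatment cut short.
- **A reader might infer that participants are unprotected until the check.** They are not. Section 1.38 has weekly team meetings, ad hoc CSO review of dose-limiting toxicities and of dose reductions for intolerance, SAE-count reviews not tied to n=20, and individual stopping rules. None of these applies the retention rule, however.
- **A reader might infer that the routine CSO report also comes too late**, because the report "that includes all AEs will occur once yearly, at the time of Continuing Review" could follow the last first dose. The section gives a rationale for yearly reporting, and the Continuing Review date is not tied to the first dose. No change is asked for there.
- **Adherence is verified mainly by pen counts at monthly visits** (section 1.20), so failures may be noticed late. This stands, and accounts for the upper end of 22 to 28.

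**Conclusion.** The point holds as a matter of timing and definition. At about 4 per month with no pause, roughly 33 to 36 of 43 will have been dosed when the check falls due, which leaves about 7 to 10 whose first dose it could prevent. This rests on uniform accrual and on the accrual rate carrying over to dosing, with or without the 43/50 yield; the figure of about 18 undosed needs the slower accrual assumed above. The mismatch between the reviewed and the stopping quantity needs no assumption.

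The practical weight is moderate. At the retention the protocol expects, the rule will rarely be met, so the gain is confined to a trial that is going badly. In that case the same decision could be reached with about 22 to 28 dosed instead of about 35 at 4 per month, assuming 60 to 70% fail.

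**What to change.** In section 1.38, keep the 50% threshold and make three changes:

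1. Use Per Protocol membership in both sentences, and name the denominator as the first 20 treated participants. The current text refers to enrolled participants.
2. Add that the CSO is notified, and the rule is treated as met, as soon as 11 of those 20 can no longer meet the Per Protocol definition. With the threshold and denominator fixed, this gives the same decision as the week-16 check on those 20, only earlier, and does not raise the chance of stopping.
3. State in section 1.32 how dose-reduced days count toward Per Protocol and which treatment length applies when the week-16 visit falls off day 112. Without this, the point at which a participant can no longer qualify is not defined.

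Section 1.38 should also say what stopping the study means for participants mid-treatment.

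The cost is small: the rewording and a running tally for 20 participants. The data are already collected through missed-dose logs and calls after 3 or more missed days (section 1.17.2.4) and pen counts at Visits 2 to 5 (section 1.20), and the team already meets weekly.
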